## 8.2 Covariates.

Patient Characteristics. We will include a socio-demographic/health questionnaire, the Tangible Social Support survey to assess the extent/quality of social connections, healthcare support will be measured using the Medication Support Survey. The Brief Test of Adult Cognition by Telephone (BTACT) and the Consumer Health Activation Index (CHAI) will also be included.

Literacy Assessment: Newest Vital Sign (NVS). Patients are given a copy of a nutrition label and asked 6 questions about how they would interpret and act on the information. Scores are classified as high likelihood of limited literacy (0-1), possibility of limited literacy (2-3), and adequate literacy (4-6).

Regimen Characteristics. Self-reported medications will be collected and grouped into drug class. These will capture important covariates that may be related to outcomes and unequally distributed among randomized subjects.

### **8.3 Fidelity (Process Measures).**

Receipt of Mobile App reminders. At each follow-up, the RC will ask whether patients used the mobile app for medication reminders.

Use of Patient Portal. At each follow-up, the RC will inquire whether patients used the portal to complete the monthly adherence assessment. We will obtain data for the number of times a patient completes the assessment.

Care Alert Notification. We will review EHR data on care alerts, nurse follow up on portal-assessed adherence concerns. The RC will also ask patients if they received follow up, by whom, and what services were provided.

### **8.4 Effectiveness Outcomes.** We will collect data on an array of knowledge, behavioral, and clinical outcomes.

Medication Adherence. Adherence will be measured using: 1) the Ask-12 Scale that assesses general medication attitudes and beliefs, 2) patient self-report of how many pills and how often each medicine was taken over the last 24 hours; 3) in-person and/or phone pill count using established guidelines employed by our team [R01HS00167; PI [name]]; 4) a biologic measure using tacrolimus levels. For 24 hour recall, correct dosing will be measured as yes/no per drug, having properly shown dose (# pills), spacing (hours between doses), frequency (times per day), and total pills/day. For pill count, we will assess adherence within drug calls. If a patient fills a prescription for a drug in a class and then switches to another drug within the same class, all prescriptions will be summed in the numerator. Adherence will be treated both continuously and dichotomously (adherent  $\geq 80\%$ ).

Biologic Measure. Medication adherence to IS medications will also be assessed by computing the standard deviation (SD) of a series of tacrolimus levels obtained for routine monitoring using validated methods. Standard clinical practice at participating centers includes routine monitoring of tacrolimus levels. Tacrolimus levels obtained during acute illness will not be included in the SD calculation. This schedule should result in >30 levels in the first 6 months post KT, 12 levels in months 6-12, 6 levels in months 13-18, 6 levels in months 19-24; and 6-8 levels per year after the second year. Laboratory methods for measurement of whole blood levels are standardized, which should reduce variability between sites. SD calculations will be made using  $\geq 4$  levels obtained over 6 months based on availability. A higher SD indicates more variability between individual measures, and is highly correlated with less stable medication intake (non-adherence) and graft rejection. A SD of the mean levels of  $\geq 2.5$  will be indicative of non-adherence. This biologic measure of adherence will be calculated at 6 month intervals to correspond to interviews.

Composite adherence measure. Each individual measure of adherence has advantages and limitations, thus we will use multiple measures as recommended by experts. Maximum

likelihood estimation will be used to create a composite adherence metric by generating a single factor score from the 5 measures of adherence.

**Regimen Knowledge:** Patient identification of drug names and indication will be assessed via assessments used previously by [name] and colleagues (ref). Patients will be asked about each of these via structured, open-ended items. Understanding of proper dosing will be assessed using the 24 hour recall task described above, but patients will be given credit if they demonstrate knowledge of how to take their medication correctly regardless of their actual behavior. From this assessment, we can also determine how patients are taking their entire multi-drug regimen, and if medications are consolidated in the most efficient manner. We will examine the total number of times throughout a 24 hour period patients indicate they will take medicine.

**Quality of Life.** We will use Patient Reported Outcomes Measurement Information System (PROMIS) Physical Function, Anxiety, Depression and Global Health subscales.

**Clinical Outcomes.** will be collected via EHR by site. Transplant-specific outcomes include: 1) change in estimated glomerular filtration rate (eGFR; ml/mn) over 24 months, 2) *Re-hospitalization*: Acute care hospitalizations 3) *Acute Rejection*: proven biopsy meeting organ-specific Banff criteria; 4) *Toxicity*: related to CNI medications (hypertension; neuro-toxic events); 5) *Infection*: CMV, BKV, bacterial infections assessed by laboratory tests and/or biopsies. *Blood pressure* (continuous SBP; control (y/n): SBP<140 & DBP<90) and *glycemic control (HbA1c)* will also be examined in those with hypertension and diabetes.

[figure not shown]

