### 9.11 Study Arms

Participants will be randomly assigned to either the TAKE IT strategy, as described in section 9.10 or usual care. Usual care refers to the normal standard clinical practices in place at either site, immediately post-transplant to the 5 years following. Northwestern and Mayo follow similar protocols for follow-up. KT recipients at both sites have lab values taken 3 times/weekly for the first 8-10 weeks post-transplant, shifting to weekly lab values for the next 3-4 months after, then monthly labs after. Both sites follow a similar tapering of weekly, to monthly to annual visits to the transplant nephrologist over the first 3 years. Protocol biopsies at both sites are taken between 3-6 months post-transplantation, at 12 then 24 months. All sites have a transplant nurse coordinator who has primary oversight of post-transplant care, full-time pharmacists and a clinical social worker. At Northwestern, the pharmacist has a standard visit with patients to review their prescribed regimen at discharge from the hospital. Social work and pharmacist visits are referrals as needed (PRN). At Mayo, both the pharmacist and social worker engage with patients only upon referral. Neither site has an active portal that engages KT recipients for any self-care support service.

**9.12 Data Sources.** Data sources for this study will include two in-person interviews and four phone interviews with participants, and Electronic Health Record chart review.

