*Power Calculation.* The sample size calculation was based on the availability of 700 transplant patients estimated by the number of transplants conducted in 2012-2014 across the two sites. With the sample size set at 610 accounting for 85-90% retention at 1 year, we present the minimum differences we will be able to detect between the intervention and usual care arms for each outcome of interest. For the main outcome of medication adherence, we estimate 45% of the sample to be non-adherent using the composite score described above taking estimates for each individual measure into account. We will have sufficient power ( $\geq 80\%$ ) to detect differences of 11% in the entire sample assuming a 5% Type I error rate. Should TAKE IT be associated with potential confounders, calculations show that an R-squared of 0.2 between predictors (a conservatively high estimate under randomization), we would still maintain 70% power to detect the 11% difference. Although adjusting for confounders would decrease variability in adherence, and increase power. Detectable differences for individual adherence measures along with estimates and effect sizes for other outcomes of interest are listed in Table 5.

Table 5. Detectable Differences in Health Outcomes between Study Arms at 1 Year

Outcome	Total (n=610) 305/arm		De Novo (n=270) 135/arm		Established (n=340) 170/arm	
	Usual Care Estimate	Minimum Difference	Usual Care Estimate	Minimum Difference	Usual Care Estimate	Minimum Difference
Primary Outcomes						
Rx Knowledge, %	50	11.3	60	15.9	45	15.1
Rx Non-adherence, %	45	11.0	35	15.2	50	15.0
Self-report, %	35	10.3	29	14.1	44	14.6
Objective (pill count), %	45	11.1	35	11.3	50	15.0
Claims (PDC), %	30	9.8	23	12.7	38	14.0
Biologic (SD Tacrolimus), %	40	10.8	30	14.3	45	14.7
Secondary Outcomes						
Quality of life, mean(SD)	46.2 (9.0)	2.0	45.8 (7.2)	2.5	49.5 (9.0)	2.7
Clinical outcomes						
$\Delta$ eGFR, mean(SD)*	-5.8 (9.0)	2.9	-3.0 (11.0)	3.8	-8.0 (15.0)	4.6
Re-hospitalizations, %	40	10.8	32	14.6	47	14.8
Systolic BP, mean(SD)**	136.7 (8.3)	2.2	138.3 (12.9)	5.1	135.0 (7.9)	2.8

\* $\Delta$  eGFR estimates over 2 years

[figure not shown]
\*\*estimate 75% of cohort has hypertension (Total: n=458, 229/arm; De Novo: n=202, 101/arm; Established: n=256, 128/arm)

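### The tacrolimus adherence measure is defined and sized only as a yes/no cut at SD 2.5, whatever the number of levels; a continuous log(SD) analysis should be added and the level counts reconciled

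*Combined protocol and SAP*

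**What the plan says.** Section 8.4 (Biologic Measure) computes the SD of routine tacrolimus levels at 6-month intervals. It says "SD calculations will be made using" at least 4 levels over 6 months, leaves out levels taken during acute illness, and treats an SD of 2.5 or more as non-adherence. There is no adjustment or weighting for the number of levels. The same section expects more than 30 levels in the first 6 months after transplant, then "12 levels in months 6-12, 6 levels in months 13-18, 6 levels in months 19-24", and 6-8 a year after the second year.

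Section 9.11 describes the laboratory schedule at both sites as three times a week for 8-10 weeks, "shifting to weekly lab values for the next 3-4 months after, then monthly labs after".

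In section 11.1 (Power Calculation), "Table 5. Detectable Differences in Health Outcomes between Study Arms at 1 Year" lists the row beginning "Biologic (SD Tacrolimus" under Primary Outcomes, as a percentage. Usual care is 40% and the minimum difference is 10.8 points with 305 per arm. The text does not say whether 40% is the rate observed under this SD rule or a rate of true non-adherence.

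**The concern.** A sample SD from a handful of values is imprecise, and its imprecision depends on how many values there are. Comparing it with one fixed cut turns that imprecision into misclassification near 2.5. Misclassification that is alike in both arms pulls the arm difference towards zero, and dichotomising also discards how far a patient lies from the cut.

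The measure matters. Aim 1 gives the individual adherence measures primary interest, Table 5 places this one among the primary outcomes, and it feeds the composite score. Because the two sections imply different level counts, the precision of the measure at the primary time point cannot be read from the plan.

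**Working it through.** **1. The plan's own figure.** Inputs from the Power Calculation: "With the sample size set at 610 accounting for 85-90% retention at 1 year", so 305 per arm; at least 80% power; 5% Type I error, taken as two-sided because the plan does not say; 40% v 40 − 10.8 = 29.2%.

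Power = Φ{[|p1 − p2| − 1.96·√(2p̄(1 − p̄)/n)] / √([p1(1 − p1) + p2(1 − p2)]/n)}.

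With p̄ = 0.346 and n = 305, the null term is 1.96 × 0.0385 = 0.0755 and the denominator is 0.0383. Power = Φ[(0.108 − 0.0755)/0.0383] = Φ(0.85) = 80.2%. The figure reproduces.

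**2. Level counts.** By section 9.11 the weekly phase ends between 8 weeks + 3 months (about month 4.8) and 10 weeks + 4 months (about month 6.3). Monthly sampling follows.

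| Time after transplant | Section 8.4 | Implied by section 9.11 |
|---|---|---|
| Months 0-6 | more than 30 | 38-46 |
| Months 6-12 | 12 | about 6-7 |
| Months 13-18 | 6 | 6 |
| Months 19-24 | 6 | 6 |
| After year 2 | 6-8 a year | 12 a year |

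The sections agree in three periods and conflict in two. Entry is 5 weeks to 24 months after transplant, so the window for the 12-month visit (study months 6-12) runs from about months 7-13 to about months 30-36 after transplant. There the count is about 12 falling to 3-4 by section 8.4, or about 6 throughout by section 9.11.

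**3. Misclassification by count.** Assume independent normal levels within a patient with true SD σ. Then P(S ≥ 2.5) = P(χ² on n − 1 df ≥ (n − 1) × 6.25/σ²). For n = 6 and σ = 2.0 the threshold is 5 × 6.25/4 = 7.81, giving 17%. For σ = 3.0 it is 5 × 6.25/9 = 3.47, giving 63% detected and 37% missed.

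| Levels | True SD 2.0, classed non-adherent | True SD 3.0, missed |
|---|---|---|
| 4 | 20% | 45% |
| 6 | 17% | 37% |
| 12 | 10% | 26% |
| 30 | 3% | 11% |

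**4. Power if 40% and 29.2% are true rates.** The documents give no between-patient distribution of true SD. Assume it is lognormal with log spread τ from 0.25 to 0.6, the same in both arms. Averaging step 3 over that distribution and putting the observed rates into the step 1 formula gives:

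| Levels | Observed difference (points) | Power |
|---|---|---|
| 4 | 5.5-8.3 | 31-61% |
| 6 | 6.6-9.1 | 41-68% |
| 12 | 8.2-10.0 | 57-75% |

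**5. Gain from a continuous analysis.** The arms differ in mean log true SD by τ × [Φ⁻¹(0.708) − Φ⁻¹(0.60)] = 0.294τ. The variance of observed log(SD) is τ² + ¼ψ′((n − 1)/2), where ψ′ is the trigamma function; the second term is 0.123 for n = 6.

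- True rates, 6 levels, τ = 0.25: difference 0.0736, SE √(2 × 0.185/305) = 0.0348, power Φ(2.11 − 1.96) = 56%.
- True rates, 6 levels, τ = 0.5: difference 0.147, SE √(2 × 0.373/305) = 0.0494, power Φ(2.98 − 1.96) = 85%.
- Over the same τ range the binary form gives 41-64%.
- Observed rates, with observed log(SD) roughly normal: standardised difference 0.294, so power is Φ(0.294 × √(305/2) − 1.96) = Φ(1.67) = about 95%, against 80% for the cut.

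**The case against.** The strongest reply is that non-adherence is defined as a computed SD of 2.5 or more, which is itself an observed classification, and that the pilot rate in section 2.4 was also observed. If the 40% has the same origin, misclassification is already inside it and 10.8 points at 80% power is correct. This stands. A reader might infer that Table 5's detectable difference is not met, but the documents do not show that.

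Three other inferences also go too far.

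- SDs from 4 and from more than 30 levels are not set side by side at 12 months. The larger count belongs to the first 6 months after transplant, and the 12-month window opens at about month 7.
- The conflict between sections does not by itself create a shortfall. Under the true-rate reading, power is below 80% even with 12 levels.
- Bias between arms is not implied. Counts follow time since transplant, which randomisation should balance, so attenuation is what to expect.

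Section 8.4 does say that adherence will be handled both continuously and dichotomously. That sentence carries an 80% threshold and closes the pill-count text, and the continuous outcomes named for the identity link in Aim 1 do not include tacrolimus SD. Section 9.11 also speaks of laboratory values in general rather than tacrolimus levels, which may explain part of the mismatch, but the plan does not say so.

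Finally, this is one component measure. Table 5's separate 11.0-point row for overall non-adherence is not tested here.

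**Conclusion.** The point holds as a loss of information and an unresolved inconsistency, not as a failed power calculation. One cut is applied whatever the count, and only the binary form is defined and sized. The two sections conflict for months 6-12 (12 v about 6-7 levels) and after year 2 (6-8 v 12 a year).

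The error rates of 17% and 37% with 6 levels rest only on independent normal levels. The power figures rest further on reading Table 5 as true rates and on a lognormal spread that the documents do not supply. On the observed-rate reading the stated 80% is unaffected. On either reading a continuous analysis does better: 56-85% against 41-64% with 6 levels (τ 0.25-0.5), or about 95% against 80%.

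In the Aim 2 series, falling counts would also move the observed usual-care rate with intake unchanged, though only slightly: from about 39% with 30 levels to about 36% with 6, if the true rate is 40%.

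**What to change.** 1. Pre-specify a continuous analysis of log(SD) at 12 months and in the Aim 2 6-month series, weighted by or adjusted for the number of levels. Keep the 2.5 cut alongside it. Demoting the cited cut to a descriptive summary would be a trade-off and is not needed.
2. Reconcile the level counts in section 8.4 with the schedule in section 9.11, and state the expected count per 6-month window once.
3. State whether the 40% in Table 5 is an observed or a true rate. If it is a true rate, restate that row for the reconciled count.
4. Say how a patient with fewer than 4 levels in a window is handled. Section 8.4's 6-8 a year is 3-4 per window, and the plan is silent. As an illustration, losing 10% of patients from this measure would take power from 80% to 76%.

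The cost is SAP wording and slightly more analysis on data already being extracted. The stated figure for this row may become less favourable.

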### 9.1 Overview & Study Design.

We will conduct a 2-arm, patient-randomized controlled trial at two large, diverse transplant centers (Northwestern University; Mayo Clinic). 700 KT recipients within 2 years of KT will be recruited and followed for 2 years (N=700 patients; n=350 per site; n=175 per study arm per site. Targeting both new and existing KT recipients is important, as adherence barriers may be different. As a result, we will aim to recruit patients

Figure 3. Study Design

with a wide spectrum of time since transplant, ranging from 5 weeks to 2 years post-transplant. In-person interviews will be conducted at baseline and 12 or 18 months (see **Figure 3**). To determine proximal effects of the TAKE IT strategy, a telephone interview will also be administered 6 weeks post-baseline. Follow-up telephone interviews will be conducted at 6, (12 or 18) and 24 months. Electronic health records will be ascertained to capture medication adherence measures and clinical outcomes (**Aim 1**). We will closely evaluate the implementation of all components of the TAKE IT strategy from launch through 2 years (**Aim 2**). Our evaluation includes several process outcomes to assess intervention reliability and sustainability (**Aim 3**). These findings will determine whether modifications to TAKE IT are necessary. Finally, we will further estimate the incremental costs of implementing and sustaining the TAKE IT strategy from the perspective of two transplant centers (**Aim 4**).

Research activities over the 5-year period will be divided into three phases: I) **Preparation** (Months 1-4); II) **Implementation** (Months 5-58), III) **Evaluation** (Months 13-60). In Phase I we will assemble our research team, orient sites, finalize study materials, and pilot test the TAKE IT strategy to ensure it is acceptable to patients, families, transplant clinicians and staff - making any necessary modifications. A randomized controlled trial will then be conducted and participants tracked for 2 years (Phase II). Our evaluation includes summative, process, and cost analyses to fully understand the clinical impact, feasibility, and costs of the TAKE IT strategy to guide dissemination efforts (Phase III).

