## 9.9 Research Procedures

Research activities will include a baseline interview, and follow-up interviews at 6 weeks, 6 months, 12 months, 18 months and 24 months. The baseline and either the 12 month or the 18 month interview will be conducted in-person\*, while the remaining interviews will be conducted via phone. To facilitate the geographical diversity of KT patients at the Mayo Clinic, measures used in the baseline and 12 month interview can be administered in-person or via phone. If a pill count needs to be completed over the phone, a pill count tray will be sent to the participant prior to the scheduled interview.

\*If the 12-month interview cannot be done in person due to the timing of clinic visits, it will be done over the phone and we will attempt to do the 18 month interview in person.

**Pilot Testing and Refinement of Study Procedures.** We will pilot test our strategy and study protocol, including the evaluation battery and patient materials, among 10 KT recipients per site who meet established patient eligibility criteria. Cognitive interviews (~45 min.) will be conducted to finalize and/or refine all study materials. We will 1) obtain average completion times for the interview, 2) elicit patient comprehension of the interview and intervention components. Necessary modifications will be made prior to full-scale implementation.

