### **9.10 Intervention: TAKE IT Strategy.**

Our strategy is a multifaceted intervention that leverages the existing resources of a transplant center and increasingly available provider and patient-facing technologies to

simplify KT recipients' role in managing complex, multi-drug regimens and monitor use over time. The goal of the TAKE IT strategy is to optimize adherence and to detect problems earlier in order to improve health outcomes – both in transplant-specific conditions and for comorbidities. This approach is multifaceted, yet highly scalable due to minimal costs and impact on existing transplant center workflow. It includes the following 4 components:

1. **A routine adherence assessment** that requests patients to periodically report upon their medication use, providing a continuous link between the transplant center and patient beyond routine in-person visits. This assessment will routinely identify patients at risk of non-adherence and categorize the nature of their adherence concern in one of the following areas: cognitive, psychological, regimen, medical, social, economic.
2. **Care Alert Notifications** directed to the transplant center nurse coordinator if an adherence related problem is identified by the routine adherence assessment, who can then activate appropriate staff to respond.
3. **Quarterly adherence reports** that will automatically calculate a coefficient of variance for patients' tacrolimus levels at routine intervals and impart results to transplant nurse coordinators.
4. **Tailored clinical support** leveraging transplant center tools to directly target the adherence-related concern identified by the routine adherence assessment. The study team will focus on leveraging existing transplant center resources, including clinical consultation with pharmacists, social workers and transplant nurse coordinators, as well as existing technological and educational tools. These tools will be bundled and initiated in response to specific patient-reported adherence concerns.

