**11.0 Data and Specimen Management:**

**11.1 Analysis Plan.**

All analyses will be performed in SAS v9.4 (SAS Institute, Cary, NC). [name] will perform analyses under the direct supervision of Drs. [name], [name] and [name]. Drs. [name] and [name] will also provide guidance.

Aim 1.

The proposed trial uses a 1:1 randomized design that assigns patients to TAKE IT or usual care within each cohort. We will accrue approximately 700 patients (350 de novo, 350 established) anticipating 90% retention in the de novo cohort (85% established) for follow-up at 1 year, leaving a minimum 525 patients for primary analyses. High retention will be supported through close follow-up, mailed reminders, birthday cards, and a newsletter. Given the clinical follow-up necessary for KT recipients, we are confident we will achieve this goal.

Regimen adherence at one year is the primary outcome of interest for Aim 1, with Rx knowledge and individual adherence measures also of primary interest. Secondary outcomes include quality of life (PROMIS outcomes and FKSI) and the clinical outcomes of change in eGFR, and any transplant-related re-hospitalization. Blood pressure control in those taking anti-hypertensive medications will also be examined. Relationships between

adherence and potential confounders (age, comorbidity, cognitive ability, regimen complexity, internet use, dose of intervention, etc.) will also be examined. For all outcomes, we will use generalized linear models (GLMs), adjusted for confounders and study site, specifying the logit link function for binary outcomes and identity link for continuous outcomes (quality of life, change in eGFR, SBP). Treatment group will be the independent variable of primary interest, with usual care specified as reference group. We will also include time since transplant at baseline (in months), baseline value of the outcome, and any potential confounding covariates noted in bivariate analysis. For outcomes measured per medication, a generalized estimating equation (GEE) approach will be employed to adjust standard errors for within-patient correlation. Should TAKE IT have an effect on outcomes, secondary analyses will examine if any of the potential confounders considered exhibit any effect modification.

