### Aim 2.

Generalized linear mixed models (GLMMs) will be used to examine intervention effects over the course of the study. Link functions will be included as described above for the GLM models. Adherence concerns may differ in the two cohorts, thus separate models will be employed for each cohort (de novo, established). Treatment group will be the independent variable of primary interest, modeled as a fixed effect with the usual care group specified as reference group. We will also include fixed effects for site (NU, Mayo), time since transplant (in months), and potential confounding covariates noted in bivariate analyses. Random participant effects for each participant will be included to account for repeated measurements nested within each participant (assuming a compound symmetry, although we will fit autoregressive structures as well, comparing fit using AIC and BIC criterion). Outcomes recorded at each interview will be analyzed by visit whereas adherence measured by tacrolimus levels, along with blood pressure control will be analyzed in 6-month intervals as described above. A time-since-transplant-by-arm interaction term will be included to examine if outcome trajectories/slopes over time differ by study arm. Since prescription knowledge and adherence will be assessed for each medication, 2-level GLMM will be used for these outcomes with medications nested in participants. For  $\Delta$  eGFR and re-hospitalization outcomes, GLM models will be used since outcomes over 2 years are summarized in a single measurement. In the de novo cohort, change in eGFR from transplant to 2 years post-transplant and # hospitalizations (any hospitalization, if rare) within 2 years post-transplant will be modeled. For the established cohort, the time period for the both measures will span from transplant to 2-year study visit. It is possible those who do not complete the 2-year visit will differ in important characteristics (e.g. cognition, comorbidity), which could bias results. We will use collected data at prior interviews to understand the extent that individuals who complete follow-up differ from those who do not. If differences are found, pattern-mixture models will be employed by classifying participants' drop-out type or pattern (e.g. completed, refused, lost to follow up, death). This variable will then be added to mixed effects models to account for differences.

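### Re-hospitalization is taken only from each site's EHR, with no described step to find admissions elsewhere, and sections 8.4 and 11.1 define it differently

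*Combined protocol and SAP*

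**What the plan says.** All references are to the combined protocol and SAP.

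**Source.** Section 8.4 states that clinical outcomes "will be collected via EHR by site". Section 9.1 agrees: "Electronic health records will be ascertained to capture medication adherence measures and clinical outcomes". Section 9.12 gives the full list: "Data sources for this study will include two in-person interviews and four phone interviews with participants, and Electronic Health Record chart review". No claims linkage, request for outside records or event adjudication is described for admissions. Sections 8.3 and 8.4 say what coordinators ask or measure at interviews, and hospital admission is not included. Table 4 places re-hospitalization under clinical outcomes and names no interview item for it.

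**Definition.** Three wordings appear:
- Section 8.4: "Acute care hospitalizations".
- Section 11.1, Aim 1: "any transplant-related re-hospitalization", with no criterion for what counts as transplant-related.
- Section 11.1, Aim 2: the number of "hospitalizations (any hospitalization, if rare"), with no transplant-related restriction.

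**Time window.** In Aim 2 the window starts at transplant in both cohorts. It ends at 2 years post-transplant for de novo patients and at the 2-year study visit for established patients. Table 5 is headed 1 year, and only the eGFR row is footnoted as covering 2 years.

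**Contact by arm.** Section 9.10 describes the TAKE IT assessment as "providing a continuous link between the transplant center and patient beyond routine in-person visits". Care alerts and tailored support follow when it finds a concern. Usual care (section 9.11) has none of these, but has frequent laboratory monitoring and a nurse coordinator.

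**The concern.** A transplant centre's record shows its own admissions. Admissions elsewhere appear only if someone at the centre learns of them and charts them. The plan has signs that patients live at a distance. Section 9.9 permits telephone administration of some measures "To facilitate the geographical diversity of KT patients at the Mayo Clinic", and section 19.2 mentions Northwestern satellite offices in Illinois and Indiana. Some outside admissions are therefore a reasonable expectation, although the plan gives no rate.

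Two consequences follow. Incomplete capture lowers the recorded event rate and the power, even when it is the same in both arms. And because the intervention itself changes how often patients and centre are in touch, capture could depend on arm, which would bias the comparison.

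The definition problem needs no assumption. All acute care admissions and transplant-related admissions are different endpoints. With no criterion for the second and no one assigned to classify events blind to arm, the choice could be made after the data are seen.

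**Working it through.** **Inputs.** From Table 5: usual care 40%, detectable difference 10.8 points, 305 per arm. From the power paragraph in section 11.1: 5% type I error and at least 80% power. Sidedness is not stated; two-sided is assumed. The TAKE IT rate is 40 − 10.8 = 29.2%.

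**Formula.** Two-proportion test with pooled variance under the null and no continuity correction:

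power = Φ{ [ |p₁ − p₂| − 1.96·√(2p̄(1 − p̄)/n) ] / √([p₁(1 − p₁) + p₂(1 − p₂)]/n) }

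**Step 1, reproduce Table 5.** With p₁ = 0.40, p₂ = 0.292, p̄ = 0.346 and n = 305, the null term is 1.96 × 0.0385 = 0.0755 and the denominator is 0.0383. So (0.108 − 0.0755)/0.0383 = 0.85 and power = 0.802. Solving for 80% power gives 10.77 points. The de novo entry (32%, 135 per arm) gives 14.64 against 14.6, and the established entry (47%, 170 per arm) gives 14.81 against 14.8. The planning figures are sound, given complete capture.

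**Step 2, equal incomplete capture.** Let s be the probability that a patient who was truly admitted is recorded as admitted, with no false positives. The recorded rates are 0.40s and 0.292s. The values of s are assumptions.

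| Capture, both arms | Recorded rates (usual care / TAKE IT) | Difference (points) | Power |
|---|---|---|---|
| 100% | 40.0 / 29.2% | 10.8 | 0.80 |
| 95% | 38.0 / 27.7% | 10.3 | 0.77 |
| 90% | 36.0 / 26.3% | 9.7 | 0.74 |
| 80% | 32.0 / 23.4% | 8.6 | 0.67 |
| 70% | 28.0 / 20.4% | 7.6 | 0.59 |

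The risk ratio stays at 0.292/0.40 = 0.73. The odds ratio, which the plan's logit link estimates, moves slightly toward 1: (0.292/0.708)/(0.40/0.60) = 0.62 at full capture, and (0.2336/0.7664)/(0.32/0.68) = 0.65 at 80%.

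**Step 3, unequal capture, run both ways.** The true rates are still 40% and 29.2%; the capture values are again assumptions.

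| Capture, usual care / TAKE IT | Difference (points) | Chance of a significant result |
|---|---|---|
| 90 / 95% | 8.3 | 0.59 |
| 80 / 90% | 5.7 | 0.34 |
| 95 / 90% | 11.7 | 0.88 |
| 90 / 80% | 12.6 | 0.93 |

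The recorded difference reaches zero only when usual-care capture is 0.292/0.40 = 0.73 times TAKE IT capture. With no true effect (40% in both arms), capture of 80% in one arm and 90% in the other gives 32% against 36%. That is a spurious 4 points with about 18% rejection in place of 5%, and its sign depends on which arm is under-captured.

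**Step 4, definitions side by side.** Section 8.4 and Aim 2 agree on scope (unrestricted) and differ in metric (admissions; count, or any if rare). Aim 1 differs in scope (transplant-related) and is binary. On timing, randomization takes place between 5 weeks and 24 months after transplant, so the Aim 2 windows include admissions before randomization. In the established cohort the window can reach 24 + 24 = 48 months. Early admissions cannot be affected by the intervention, so they add noise. The period to which Table 5's 40% refers is not clear.

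**The case against.** The strongest objection is that the documents do not show that anything is missed. They give no rate of admission elsewhere and do not say whether the site charts include outside records. Telephone interviewing at Mayo and satellite offices at Northwestern do not show where recipients are admitted. The interview instrument is not in the documents and Table 4 is partly unreadable as extracted, so it is fair to say that an admissions question is not described, but not that none is asked. This stands. The capture values above are assumptions, not estimates.

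A reader might go further and infer that admissions are missed more often in usual care, so that the plan hides a benefit of TAKE IT or makes a null effect look like harm. The documents do not support that. No passage says that capture differs by arm. The TAKE IT assessment collects adherence concerns, not admissions, and alerts follow only when a concern is found. Usual care already has laboratory tests three times a week, then weekly, then monthly, protocol biopsies and a nurse coordinator overseeing care (section 9.11). Extra contact makes unequal capture possible; its size and sign are unknown.

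The remedy also carries risk. Section 8.3 has coordinators ask about portal use and clinic follow-up, so interviewers may learn the arm. Participants who stop responding are withdrawn (section 13.1) and would contribute EHR data only.

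None of this answers the definition conflict.

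**Conclusion.** The point holds for a secondary outcome, in two parts.

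First, the site EHR is the only source named for re-hospitalization, and no step to find admissions elsewhere is described. If capture is incomplete, power falls from 0.80 to about 0.74 at 90% capture and about 0.67 at 80%, even when the arms are captured equally. These figures assume a two-sided 5% test, Table 5's rates and no false positives. Arm-dependent capture is a possibility of unknown direction that could attenuate or exaggerate the effect. It should not be reported as a bias against TAKE IT.

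Second, section 8.4, Aim 1 and Aim 2 do not describe the same outcome or period, and this is visible on the page without any assumption.

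Table 5's arithmetic is correct, and the primary outcome, adherence at one year, is unaffected.

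**What to change.** 1. **Capture.** Add one fixed question, worded identically in both arms, to each existing follow-up interview (6 weeks; 6, 12, 18 and 24 months): any overnight admission at any hospital since the last interview, with date and hospital. Combine the answers with EHR events. Confirm outside admissions from records where the authorization allows; section 25.3 mentions authorization for record review, but whether it reaches other hospitals cannot be checked here. Report an EHR-only sensitivity analysis, because interviewers may learn the arm and non-responders have EHR data only.

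2. **Definition.** Before analysis, reconcile section 8.4, Aim 1 and Aim 2 to one definition and one time window, and say whether admissions before randomization count. All acute care admissions is the simpler choice: it needs no causal judgement and matches the scope of section 8.4 and Aim 2. Any transplant-related subset should have a written criterion and be classified from records with the arm removed. State the period to which Table 5's 40% refers.

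**Cost.** About a minute per interview, some record requests and a wording change in the plan. The downsides are recall error, possible unblinded elicitation, and the inclusion of admissions unrelated to adherence.
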